## 6.3.1. Adverse Events Based on Signs and Symptoms

Each AE should be recorded to represent a single diagnosis. Accompanying signs (including abnormal laboratory test values or ECG findings) or symptoms should NOT be recorded as additional AEs. If a diagnosis is unknown, sign(s) or symptom(s) should be recorded as an AE(s).

### **6.3.2.** Adverse Events Based on Tests or Examinations

Changes in laboratory test values or ECG parameters are only considered to be AEs if they are judged by the Investigator to be CS (ie, if some action or intervention is required or if the Investigator judges the change to be beyond the range of normal physiological fluctuation).

If abnormal laboratory test values or ECG findings are the result of pathology for which there is an overall diagnosis (eg, increased creatinine levels in renal failure), only the diagnosis should be reported as an AE.

## **6.3.3.** Follow-up of Unresolved Adverse Events

All drug-related (Section 6.3.4) AEs, including CS abnormal laboratory test results reported or observed during the study, must be followed to resolution (either return to baseline or within normal limits). All other AEs or non–drug-related abnormal laboratory results will be followed through the final visit (ie, EOS or early termination). Information to be collected includes type of event, date of onset, date of resolution, Investigator-specified assessment of severity and relationship to study drug, seriousness, as well as any action taken.

## 6.3.4. Assessment of Causality

The relationship of an AE to the administration of the study drug is to be assessed according to the following definitions:

Unrelated: This relationship suggests that there is no association between the study drug and the reported event.

Unlikely: This relationship suggests that the temporal sequence of the event with study drug administration makes a causal relationship improbable and/or other factors also provide plausible explanations.

Possible: This relationship suggests that treatment with the study drug caused or contributed to the AE. That is, the event follows a reasonable temporal sequence from the time of study drug administration and/or follows a known response pattern to the study drug but could have been produced by other factors.

Probable: This relationship suggests that a reasonable temporal sequence of the event with study drug administration exists and based upon the known pharmacological action of the drug, known or previously reported adverse reactions to the drug or class of drugs, or judgment based on the Investigator's clinical experience, the association of the event with study drug administration seems likely.

Definitely: This relationship suggests that a definite causal relationship exists between the study drug administration and the AE, and other conditions (eg, concurrent illness, progression/expression of disease state, or concurrent medication reaction) do not appear to explain the event.

Not Applicable: AE occurred prior to administration of first dose of study drug.

## 6.3.5. Assessment of Severity

The Investigator will grade the severity of the AEs as mild, moderate, or severe using the following definitions:

Mild: Symptoms causing no or minimal interference with usual social and functional activities

Moderate: Symptoms causing greater than minimal interference with usual social and functional activities

Severe: Symptoms causing inability to perform usual social and functional activities

## **6.4.** Reporting of Serious Adverse Events

## **Initial Reports**

Any AE, occurring from the time of consent until the final visit or 30 days following final study dose for subjects who terminate early, that meets the criteria of serious according to the previously described criteria must be reported within 24 hours from the time when site personnel first learn about the event. To report the SAE, fax or email the completed SAE form along with any supporting documentation (eg, subject discharge summary or autopsy reports) to (fax number and email listed below in Table 5) within 24 hours of awareness.

### **Follow-up Reports**

The Investigator must continue to follow the subject until the SAE has subsided or until the condition becomes chronic in nature, stabilizes (in the case of persistent impairment), or the subject dies.

Within 24 hours of receipt of new information, the updated follow-up SAE form, along with any supporting documentation (eg, subject discharge summary or autopsy reports), should be faxed or emailed to Sponsor/designee (Table 5).

The Sponsor or its designee will notify regulatory agencies of any fatal or life-threatening unexpected events associated with the use of the study drug as soon as possible, but no later than 7 calendar days after the initial receipt of the information. Initial notification will be followed by a written report within the timeframe established by the appropriate regulatory agency. For other

SAEs that do not meet the fatal or life-threatening unexpected criteria but are reported to be associated with the study drug, the Sponsor or its designee will notify the appropriate regulatory agencies in writing within the timeframe established by those regulatory agencies. The Sponsor or its designee will provide copies of any reports to regulatory agencies regarding serious and unexpected SAEs to the Investigators for their information and submission to their IRB, as appropriate.

Investigators are responsible for informing their IRB of any SAEs at their site, as appropriate. The DMC will review all safety data in an unblinded manner throughout the study and make recommendations as appropriate. All SAE correspondence with regulatory authorities or IRBs must be submitted to the Sponsor or its designee for recording in the study file.

## 6.5. Overdose

An overdose is defined as a subject administering any dose as non-compliant (more than 120% of expected study drug visit to visit). Overall, the RTA 901 toxicity program has identified the liver and kidney as target organs at doses producing systemic exposures (based on AUC) at least 50-fold above those observed in humans at the highest planned clinical dose of 80 mg. The adverse effects on liver and kidney identified in GLP toxicity studies were associated with readily monitorable and standard clinical pathology evaluations and were reversible after drug discontinuation. Overall, safety margins of > 40-fold were established, based on systemic exposures (ie, AUCs) at the no observed adverse effect levels from the 3-month GLP toxicity studies in mice and monkeys and the systemic exposure (ie, AUC) at the highest dose in human subjects (ie, 80 mg).

Any overdose is required to be reported within 24 hours either as an AE or SAE. Overdose does not automatically make an AE serious, but if the consequences of the overdose are serious and meet the serious criteria (Section 6.2), the event must be reported as an SAE according to Section 6.4.

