## **2.2.1.2.** Safety

• Frequency, intensity, and relationship to study drug of adverse events (AEs) and SAEs and change from baseline in the following assessments: physical examinations, vital sign measurements, ECGs, clinical laboratory measurements, and body weight

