# 5.5. Schedule of Assessments

Table 4 lists the overall schedule of assessments for the study.

Table 4: Schedule of Assessments (Part 1 & 2)

Study Period	udy Period Screening Period Run-in Period Treatment Period						Follow-up Period				
Study Visit	Screening	Run-in	Day 1 c	Week 1	Week 2	Week 4			Week 10	Week 12 / EOT	Week 16 / EOS d
Study Day	Day -28 to -15	Day-14 to -1 (± 2)	Day 1	Day 8 (± 2)	Day 15 (± 2)	Day 29 (± 2)	Day 43 (± 2)	Day 57 (± 2)	Day 71 (± 2)	Day 85 (± 2)	Day 113 (± 2)
Administrative Procedures:											
Informed Consent	X										
Run-in Inclusion/Exclusion e	X	X									
Demographics	X										
Medical History	X										
Prior and Concomitant Medications	X	X	X	X	X	X	X	X	X	X	X
Adverse Events f	X	X	X	X	X	X	X	X	X	X	X
Electronic Diary Set-up	X										
Clinical Procedures/Assessments:											
Height Measurement g	X										
Weight Measurementh	X	X	X	X	X	X	X	X	X	X	X
Comprehensive Physical Examination	X		X							X	X
Targeted Physical Examination i		X		X	X	X	X	X	X		
ECG	X		$X^{j}$	X						X	X
Vital Sign Measurements	X	X	X	X	X	X	X	X	X	X	X
MNSI	X										
Laboratory Procedures/Assessments:											
Pregnancy Tests for Females of Child-bearing Potential k	X		X	X	X	X	X	X	X	X	X
FSH l	X										
Serology (Hepatitis and HIV Screening)	X										
COVID-19 Test	X		X								
Drug of Abuse and Cotinine Screen	X										
Clinical Chemistry	X		X	X	X	X	X	X	X	X	X
INR	X		X	X	X	X	X	X	X	X	X
Hematology	X		X	X	X	X	X	X	X	X	X
Urinalysis and Microscopy	X		X	X	X	X	X	X	X	X	X
HbA1c	X					X		X		X	X
Fasting Lipid Profile n	X					X		X		X	X

Study Period	Screening Period a	Run-in Period b	Treatment Period						Follow-up Period		
Study Visit	Screening	Run-in	Day 1 c	Week 1	Week 2	Week 4	-	Week 8	Week 10	Week 12 / EOT	Week 16 / EOS d
Study Day	Day -28 to -15	Day-14 to -1 (± 2)	Day 1	Day 8 (± 2)	Day 15 (± 2)	Day 29 (± 2)	Day 43 (± 2)	Day 57 (± 2)	Day 71 (± 2)	Day 85 (± 2)	Day 113 (± 2)
Study Drug Procedures:											
Randomization Inclusion/Exclusion			X								
Randomization			X								
Dispense Study Drug		X	X			X		X			
Study Drug Administration o		X	X p	X	X	X	X	X	X	X	
Collect / Review Study Drug			X			X		X		X	
Patient Reported Outcome Assessments:											
NPRS q	X	X	X	X	X	X	X	X	X	X	X
DSIS r	X	X	X	X	X	X	X	X	X	X	X

Abbreviations:

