## 6.1. Definition of Adverse Event

An AE is defined as any untoward medical occurrence in a subject regardless of its causal relationship to study drug. An AE can be any unfavorable and unintended sign (including any CS abnormal laboratory test result), symptom, or disease temporally associated with the use of the study drug, whether or not it is considered to be study drug related. Included in this definition is any newly occurring event or previous condition that has increased in severity or frequency since the administration of study drug.

The definition above, provided for in the good clinical practice (GCP) International Council for Harmonisation of Technical Requirements for Pharmaceuticals for Human Use (ICH) Guideline E6, is being extended for the purpose of Reata studies to include any events, intercurrent diseases and accidents observed while the subject is on study, ie, during the actual Treatment Period, as well as during drug-free, pre- and post-Treatment Periods.

All AEs observed or reported by the subject during the study (from the time of consent until the final visit or 30 days following final study dose for subjects who terminate early) must be reported, regardless of their relationship to study drug or their clinical significance. All conditions present prior to time of consent should be documented as medical history.

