# 7.5. Study Drug Administration

Subjects must self-administer 1 capsule orally from each of the bottles included in their study drug kit QD, beginning at Run-in through the end of the Treatment Period, as indicated in Table 4. Each dose of study drug should be administered at approximately the same time each day and will be recorded in the e-diary. All doses should be taken in an early fasted state, defined as having no food within at least 2 hours prior to study drug administration and 1 hour following study drug administration.

A vomited dose must not be replaced. A double dose (eg, missed dose from previous day and dose for current day) must not be taken.

It is the responsibility of the Investigator or designee to provide clear instructions to the subject regarding the number and type of capsules to be ingested at each study drug administration timepoint listed in Table 4. Subjects must be instructed to continue taking study drug once daily through Week 12 unless:

- 1. The subject has been otherwise instructed by the Investigator, or
- 2. The subject has been formally discontinued from study drug.

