## 7.6. Treatment Compliance

The Investigator or his/her designated and qualified representatives will only dispense study drug to subjects enrolled in the study in accordance with the protocol. Subjects should administer study drug exactly as instructed by the site. Non-compliance is defined as taking less than 80% or more than 120% of expected study drug during any evaluation period (visit to visit).

Subjects should record in the e-diary all administered and missed doses of study drug. The reason for a missed dose should be recorded in the e-diary. A missed dose includes drug holidays and temporary study drug discontinuations. Subjects will be asked to return all unused study drug (study drug bottles and any unused capsules).

Refer to Section 5.1.7 for compliance related to PRO completion via the e-diary.

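### Protocol Section 6.5 defines overdose only by the visit-to-visit compliance total, so a one-day double dose, or a triple dose in a 14-day interval, can escape the 24-hour report; the safety effect is small

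*Protocol*

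**What the plan says.** Protocol Section 6.5 defines the event: "An overdose is defined as a subject administering any dose as non-compliant (more than 120% of expected study drug visit to visit". It then attaches the reporting duty: "Any overdose is required to be reported within 24 hours either as an AE or SAE".

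Section 7.6 sets the compliance limits with the same upper figure and the same period: "Non-compliance is defined as taking less than 80% or more than 120% of expected study drug during any evaluation period (visit to visit". It also provides a daily record: "Subjects should record in the e-diary all administered and missed doses of study drug".

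Section 7.5 sets the regimen, one capsule from each bottle in the kit once a day, and adds: "A double dose (eg, missed dose from previous day and dose for current day) must not be taken". It does not call a double dose an overdose or ask for it to be reported as one.

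Section 6.1 describes an adverse event differently from an overdose: "An AE is defined as any untoward medical occurrence in a subject regardless of its causal relationship to study drug".

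In the schedule of assessments (Section 5.5, Table 4), treatment visits fall on Days 1, 8, 15, 29, 43, 57, 71 and 85, with ±2 days on each visit after Day 1. The row "Collect / Review Study Drug" is marked only on Day 1 and at Weeks 4, 8 and 12.

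The SAP has no overdose definition. Its Section 3.6 uses the 80% and 120% limits only to exclude subjects from the per-protocol set.

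**The concern.** A compliance ratio asks whether the right amount was taken over a period. An overdose rule asks whether too much was taken at once. Using the first for the second has three consequences.

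- **Dilution.** The normal days in the interval offset the excess, so visit spacing decides whether the same event counts, not exposure.
- **Ordering.** Over 14 days, three doses in one day are not an overdose, but three separate double doses are.
- **Timing.** The total is settled only when the interval closes, which fits poorly with a 24-hour report.

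What would be lost is the prompt report of an excess without symptoms or serious consequences. This matters mainly in the 80 mg arm. Three doses there exceed 160 mg, the highest single dose that the protocol's Version 2 to 3 summary of changes describes as well tolerated in healthy volunteers.

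**Working it through.** The 120% is a set limit, so the plan has no derived figure to reproduce. The check is a direct count.

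**Inputs.** One dose a day (Sections 7.1 and 7.5); overdose if strictly above 120% of expected drug (Section 6.5); visit days and windows from Table 4.

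**Formula.** For an interval of d days with m missed doses and n doses taken on one day, the share of expected drug is (d − 1 − m + n)/d.

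**Nominal intervals, no missed doses (m = 0):**

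| Interval | 2 doses in one day | 3 doses | 4 doses |
|---|---|---|---|
| 7 days | 8/7 = 114.3%, not counted | 9/7 = 128.6%, counted | 10/7 = 142.9%, counted |
| 14 days | 15/14 = 107.1%, not counted | 16/14 = 114.3%, not counted | 17/14 = 121.4%, counted |
| 28 days | 29/28 = 103.6%, not counted | 30/28 = 107.1%, not counted | 31/28 = 110.7%, not counted |

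The 7- and 14-day rows take every clinic visit as closing an interval. The 28-day row takes drug review as closing it. In that row six doses in one day give 33/28 = 117.9% and do not count; seven give 34/28 = 121.4% and do.

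**Make-up double dose.** With m = 1 and n = 2 the share is (d − 1 − 1 + 2)/d = 100% at any d. This is the example that Section 7.5 forbids.

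**Ordering.** Three separate double doses in 14 days give (14 + 3)/14 = 121.4%, which counts. Three doses in one day give 114.3%, which does not.

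**Visit windows.** Day 1 to Week 1 runs 5 to 9 days, Week 1 to Week 2 runs 3 to 11 days (7 ± 4), and a nominal 14-day interval runs 10 to 18 days (14 ± 4).

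- A double dose counts if (d + 1)/d > 1.2, so only if d < 5: 4/3 = 133.3% and 5/4 = 125.0% count, 6/5 = 120.0% does not. Only Week 1 to Week 2 can be that short.
- A triple dose counts if (d + 2)/d > 1.2, so only if d < 10: 11/9 = 122.2% counts, 12/10 = 120.0% does not. It therefore never counts in a nominal 14-day interval, but always counts between Day 1 and Week 1.

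**Amounts.** In the 80 mg arm, 2 × 80 = 160 mg and 3 × 80 = 240 mg, the latter 240/160 = 1.5 times the 160 mg single dose. In the 10 mg arm, 3 × 10 = 30 mg, below the 80 mg daily dose. Placebo carries no exposure.

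**The case against.** The strongest reply is that the rule is lenient by choice and that other safeguards cover the risk. Section 6.5 itself states exposure margins above 40-fold at 80 mg, with liver and kidney findings that were reversible and could be monitored. Symptoms after an extra dose are still adverse events, and serious consequences still go through the 24-hour route of Section 6.4. Chemistry and INR are drawn at every treatment visit, and the DMC sees unblinded safety data. All of this stands and limits the size of the point. A reader might infer that subjects face a material undetected hazard, or that an extra dose goes unrecorded. The documents do not support either: doses are entered in the e-diary, and SAP Section 5.4 lists an incorrect dose among possible protocol deviations.

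Second, Section 7.5 does set a per-day intake rule. That is right. What is missing is a per-day trigger for the overdose report, not a per-day dosing instruction. The words about any dose in Section 6.5 might suggest a per-dose reading, but the parenthesis ties them to the interval total.

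Third, the 7- and 14-day cut-offs depend on reading every clinic visit as the end of an interval. This also stands. The other reading, by drug review, widens the gap and so does not rescue the rule.

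Fourth, a reader might infer that make-up doses now inflate the adverse event counts in the primary safety endpoint, "Frequency, intensity, and relationship to study drug of adverse events (AEs) and SAEs". They do not: a make-up double dose scores 100% and is outside the present rule. That problem would arise only from a stricter definition, so the adverse event wording has to change with it.

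**Conclusion.** The point holds as a small, inexpensive improvement in safety reporting. Section 6.5 misclassifies an acute excess because it borrows a cumulative compliance limit. At nominal spacing a one-day double dose is never reportable as an overdose, and a one-day triple dose is not reportable in a 14-day interval. A triple dose in an otherwise compliant 7-day interval is caught, so it would be wrong to say that triple doses always escape.

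These cut-offs assume that every clinic visit closes an interval and that all other doses are taken as planned; each missed dose in the interval lowers the total further. The direction of the finding does not depend on how the interval is read, but the exact cut-offs do. Sample size, power, type I error and the efficacy analysis are not affected.

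**What to change.** - **Section 7.6:** keep the 80% and 120% visit-to-visit limits, for compliance only.
- **Section 6.5, definition:** define overdose as intake above the assigned once-daily dose in one day, that is, more than one capsule from any bottle in the kit. Report it to the sponsor within 24 hours of the site becoming aware, from the e-diary or from the subject. The clock then matches Section 6.4, and one rule serves all blinded arms.
- **Section 6.5, consequential edit:** record an asymptomatic excess as an overdose or dosing error, and as an AE or SAE only if it has clinical consequences. This fits Section 6.1 and keeps newly reportable make-up doses, including placebo, out of the adverse event counts.

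**Cost.** Two sentences change, and the case report form needs a place for a dosing error. There will be extra reports of minor excesses, mainly make-up double doses, across all arms. The documents do not say whether the e-diary accepts a second dose on one day or how often sites review it, so this must be checked. The present rule already relies on the e-diary at Weeks 1, 2, 6 and 10, where no drug review is scheduled. If a site learns of the excess only at the next visit, the gain in promptness is small.

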# 6.6. Pregnancy

During the study, all female subjects must be instructed to contact the Investigator immediately if they suspect they might be pregnant (eg, late or missed menstrual period). Male subjects must be instructed to contact the Investigator if a sexual partner suspects she may be pregnant.

If a subject or Investigator suspects that the subject may be pregnant, the study drug must be withheld until the results of a serum pregnancy test are available. If pregnancy is confirmed with a serum pregnancy test, the subject must discontinue taking study drug and be discontinued from the study (Section 4.6.3).

Pregnancy in a study subject must be reported to the responsible safety party within 1 business day of the site becoming aware of the pregnancy. Information regarding a pregnancy occurrence in a study subject and the outcome of the pregnancy will be collected. The Investigator must follow a pregnant subject or the pregnant female partner of a male subject (if consenting) and report follow-up information regarding the course of the pregnancy, including perinatal and neonatal outcome. Infants resulting from such pregnancies should be followed for a minimum of 8 weeks. The Sponsor or its designee may contact the Investigator to request additional information throughout the course of the pregnancy.

Pregnancy in a study subject is not considered an AE. However, the following pregnancy outcomes must be considered SAEs and will require additional reporting in the eCRF and on an SAE form:

- Congenital anomaly/birth defect;
- Stillbirth; or
- Spontaneous miscarriage.

## 6.7. Methods of Birth Control

During Screening, while taking study drug, and until 30 days following administration of the final dose of study drug, females of child-bearing potential must practice 1 of the following highly effective methods of birth control:

- Use of hormonal contraceptives associated with inhibition of ovulation (oral, parenteral, intravaginal, or transdermal) as prescribed;
- Use of a non-hormonal intrauterine device with appropriate re-insertion period (as prescribed);
- Use of an intrauterine hormone-releasing system as prescribed;
- Vasectomized partner (with vasectomy performed at least 6 months prior to Screening with the appropriate post-procedure documentation of surgical success). Partner *must* be the sole partner for that subject;
- Abstain from sexual intercourse completely. Complete abstinence from heterosexual intercourse is only acceptable if it is the preferred and usual lifestyle of the individual. Periodic abstinence is not permitted.

In addition, female participants should not donate eggs for the duration of the study and for at least 30 days after their last dose of study treatment.

During Screening, while taking study drug, and until 30 days after the final dose of study drug, fertile males who have female partners of child-bearing potential must practice 1 of the following methods of birth control:

- Partner contraception methods; *must* be the sole partner for that subject:
  - Use of a non-hormonal intrauterine device with appropriate re-insertion period (as prescribed);
  - Use of hormonal contraceptives associated with inhibition of ovulation (oral, parenteral, intravaginal or transdermal) as prescribed;
  - Use of an intrauterine hormone-releasing system as prescribed;
  - Surgically sterile partner (bilateral tubal ligation, hysterectomy, bilateral salpingectomy, or bilateral oophorectomy); fallopian inserts with confirmed blockage (eg, x-ray, ultrasound);
  - Reproductive potential has been terminated by radiation;

- Postmenopausal (defined as no menses for at least 1 year without an alternative medical cause).
- Abstain from sexual intercourse completely. Complete abstinence from heterosexual intercourse is only acceptable if it is the preferred and usual lifestyle of the individual. Periodic abstinence is not permitted.

In addition, male participants should not donate sperm for the duration of the study and for at least 90 days after their last dose of study treatment.

